#### *Risks and Benefits*

Answering Questions during Enrollment or at Follow-up: Women may feel uncomfortable answering questions about breastfeeding and birth control. Women can choose not to answer questions that make them feel uncomfortable. All interviews that are done in the hospital setting will be done in a private room (all patient rooms on Labor and Delivery or on Postpartum are private), with the door closed. For follow-up, women will be able to choose if they complete the questionnaire over the phone, at a time convenient for them, or via a web-based HIPPA secure survey generated through REDCaps.

Insertion of the Implant: Choosing to enroll in this study means that women will be assigned to one of three time points for contraceptive implant initiation after delivery, as opposed to receiving it at a time of their own choosing. Currently all women delivering at Weiler are routinely offered immediate postpartum initiation of the contraceptive implant at all the time points being studied as a part of this protocol. Insertion of the implant is a very safe procedure with risks comparable to a blood draw or IV placement. Having the implant placed as part of this study does not confer any additional or different risk associated with the insertion procedure than if the implant was placed at any other time.

Breastfeeding: Currently all available data regarding breastfeeding and the implant demonstrate that immediate postpartum initiation of the implant does not have any effect on breastfeeding establishment, success, or duration. Prior studies have not specifically looked at women who have risk factors for low milk supply, however, the CDC, ACOG, and institutional guidelines do support the use of the implants in the immediate postpartum period for this population. Currently the routine practice at Montefiore is that all women are offered immediate postpartum placement of a contraceptive implant. All women are counseled that current evidence does not demonstrate that the implant would have any effect on breastfeeding, but that data is limited, especially for women with risk factors for low milk supply. This study does not confer any additional risk to breastfeeding women over our current routine practice but will allow those women who are enrolled into the trial to have more ready access to providers and community resources for breastfeeding support.

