## **Research Design and Methods**

### *Research Design and Study Subjects*

This will be a three-armed randomized non-inferiority study of women delivering at the Weiler Hospital of the Albert Einstein College of Medicine who plan to breastfeed, have known risk factors for low milk supply, and who intend to use the contraceptive implant postpartum. Women will be randomized to one of three groups: device placed within 30 minutes of placental delivery, 24-72 hours postpartum, or 6 or more weeks postpartum. All study activities will adhere to the CONSORT guidelines for reporting randomized trials. Women will be assessed at enrollment, 1-5 days postpartum, 6 weeks, 3 months and 6 months postpartum.

Eligibility Criteria will include:

- 1) Live pregnancy of at least 24 weeks gestation
- 2) Intention to use a contraceptive implant postpartum
- 3) Intention to use a non-hormonal bridging method of contraception until a contraceptive implant can be placed
- 4) 18 years of age or older
- 5) English or Spanish speaking
- 6) Women will be enrolled either during prenatal care or upon admission to Labor and Delivery.
- 7) Absence of pain. Among women who are being enrolled on Labor and Delivery MUST fall into one of the three following categories:

- Women presenting for induction of labor. Women will be approached and enrolled prior to the onset of labor.
- Women presenting for a planned cesarean delivery. Women will be approached and enrolled prior to entry into the operating room.

- Women who have an Epidural in place for management of pain. Prior to engaging in a discussion regarding the study protocol, women will be asked if they are experiencing any pain, and if the answer is yes, they will not be eligible for entry into the study.

7) Presence of at least one of the following conditions known to be a risk factor for low milk supply:

- Expected delivery prior to 37 weeks
- Obesity (pre-pregnancy BMI >35)
- Polycystic Ovarian Syndrome
- Diabetes (gestational or pre-gestational)
- Self-reported difficulty with low milk supply in past

*Setting and Population*

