Women will be enrolled, consented and randomized on Labor and Delivery, prior to delivery. The study brochure will be included in the standard educational materials provided to all women on admission to Labor and Delivery. All enrollment and screening will be done in private labor and delivery rooms and all measures will be taken to ensure patient privacy. Women will be explicitly told that their participation in this trial is voluntary and that they have the option of receiving a contraceptive implant at any of the time points included in this study if they decline participation in this trial. Only co-investigators who have completed CITI training and who are intimately familiar with the study protocol will be approaching or enrolling patients into the trial.

During the informed consent process, women will receive standardized contraceptive counseling, including information about the contraceptive implant and its potential effects on breastfeeding. Women who are eligible for the trial and interested in participating will be enrolled and randomized in a 1:1:1 ratio to one of the three groups to determine their timing of contraceptive implant placement. Participants will be assigned using computer-generated random numbers in blocks of varying sizes with strict allocation concealment using sequentially numbered opaque envelopes. Women will be informed of their randomization group at the time of enrollment into the trial.

Women randomized to receive the implant within 30 minutes of delivery will have the implant placed in the delivery room or operating room within 30 minutes of placental delivery. Placement of the implant will not interfere with any skin-to-skin interactions that are currently routinely encouraged for the mother and infant after every delivery. Women randomized to receive the implant within 1-3 days of delivery will have their implant placed on the postpartum unit more than 24 hours after delivery, but prior to discharge from the hospital. Women randomized to receive the implant at 6 or more weeks postpartum will be scheduled for an outpatient visit with the family planning clinic at 6-8 weeks postpartum for implant placement.

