Successful recruitment, follow-up and retention represents the most significant challenge to the completion of this project. The population of women we intend to enroll is socioeconomically disadvantaged and has high rates of non-adherence to postpartum care. Only 43% of women who deliver at Weiler attend a postpartum visit within 12 weeks of delivery. While this is a difficult to study population, they are also the women who may benefit the most from access to immediate postpartum contraception as attendance at a postpartum visit clearly represents a significant barrier to care for most of these women. [name] has a proven track record of successfully following women in this specific community in the immediate postpartum period. She served as the principal investigator on a set of trials examining the effects of a primary care intervention on breastfeeding outcomes. During these trials she successfully recruited and followed a cohort of postpartum women from our institution and has developed a set of proven strategies for ensuring high levels of retention among a population of women with historically high attrition rates. We intend to use the following specific strategies:

- 1) Strong Rapport with the Participants

- a) Research Coordinators (RC) will visit the women enrolled in to the study at least twice during their postpartum admission to encourage rapport building
- b) RCs will maintain regular contact with participants throughout the follow up period via text and email. Reminders will be emailed and texted in the weeks prior to any scheduled follow-up.
- c) RCs will send birthday ECards for all the study participants.
- d) Participants will be provided with business cards and other items (pens, magnets) containing the RC cell phone number and study contact information.

2) Convenience for the Participants

- a) Brief- Upon final pilot testing the follow-up questionnaires will take < 15 minutes to complete.
- b) Flexible methods- Participants will have the option of completing the follow-up questionnaires via phone or web survey.
- c) Flexible hours- Women will indicate their preferred times to be called, including nights and weekends
- d) Bilingual- All written study materials will be available in both English and Spanish. The RCs will be bilingual.

3) Educational and Appropriate Materials and Questionnaires

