#### *Sample Size*

To achieve specific aim 1, we chose a non-inferiority margin of an additional 8 hours to achieve lactogenesis II, as this would be clinically relevant. In order to achieve 80% power, using a one-sided Type 1 error of 5%, and with a standard deviation in time to lactogenesis of up to 18 hours, 63 women would be needed in each group, for a total of 189 women.

To achieve specific aim 2, larger sample size will be required. Prior studies in our population have found that breastfeeding continuation rates at 6 months postpartum are 27%. Assuming a non-inferiority margin of 15%, to achieve 80% power using a one-sided Type 1 error of 5%, we would need to enroll 109 women per group, for a total of 327 women total. Assuming a 15% loss to follow up rate, we will enroll 375 women total, 125 in each group. This recruitment goal will be met over an 18 month time period and is attainable based on the approximately 60 implants placed each month on the Labor and Delivery and Postpartum units.

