#### *Analysis Plan*

The following outcomes will be evaluated using T-tests and include: exclusive breastfeeding continuation, any breastfeeding continuation, implant continuation. Additional secondary outcomes include side effects and tolerability of the implant, vaginal bleeding patterns, and contraceptive use. To evaluate these secondary outcomes between the two groups we will use the T-test, Wilcoxon Rank Sum test, Chi-squared test, or Fisher's exact test as appropriate.

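### This non-inferiority trial of insertion timing plans no comparison among women treated as assigned, so any delayed-arm crossover to early insertion would favour a non-inferiority finding

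*Combined protocol and SAP*

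**What the plan says.** - **Design.** Research Design and Study Subjects states: "This will be a three-armed randomized non-inferiority study of women delivering at the Weiler Hospital". The Recruitment section has women "enrolled and randomized in a 1:1:1 ratio to one of the three groups" before delivery and tells them their group at enrolment.
- **Exposure.** The arms differ only in when the implant is placed. Recruitment says: "Women randomized to receive the implant within 30 minutes of delivery will have the implant placed in the delivery room or operating room". The second arm is treated on the postpartum unit after 24 hours and before discharge. The third is booked for a family planning clinic visit at 6–8 weeks.
- **Routine care.** Risks and Benefits says: "Currently the routine practice at Montefiore is that all women are offered immediate postpartum placement of a contraceptive implant".
- **Clinic attendance.** Recruitment, Follow-up and Retention (under Study Procedures) says: "Only 43% of women who deliver at Weiler attend a postpartum visit within 12 weeks of delivery".
- **Margins.** For Aim 1, Sample Size says "we chose a non-inferiority margin of an additional 8 hours to achieve lactogenesis II". For Aim 2 the margin is 15 percentage points on a 27% breastfeeding rate at 6 months. Both use one-sided 5% error and 80% power. The only allowance is 15% for loss to follow-up.
- **Analysis.** The Analysis Plan is one short paragraph: "The following outcomes will be evaluated using T-tests and include: exclusive breastfeeding continuation, any breastfeeding continuation, implant continuation", followed by a list of tests for the secondary outcomes. It names no analysis set and no rule for a woman whose implant is placed outside her window or never. Specific Aims describes the groups by randomised assignment. Neither Study Procedures nor Data Quality Checks lists actual insertion time among the variables.

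**The concern.** In a superiority trial, crossover between arms costs power, so analysing women as randomised is the cautious choice. In a non-inferiority trial it works the other way. If women in the 6-week arm receive the implant in hospital, the arms become more alike in exposure. A true delay in lactogenesis or a true fall in breastfeeding then appears smaller than it is, and the test is more likely to declare non-inferiority.

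The setting makes this worth guarding against. Early placement is available on the same units, women know their arm before delivery, and the delayed arm depends on an outpatient visit that the protocol itself treats as a barrier. The results are meant to inform guidelines for women at risk of low milk supply, so a false declaration of non-inferiority is the costly error.

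**Working it through.** **Inputs from Sample Size:** Aim 1 margin 8 h, SD 18 h, 63 per arm; Aim 2 rate 27%, margin 15 points, 109 per arm; one-sided 5%, 80% power; 125 enrolled per arm with 15% loss, so 125 × 0.85 ≈ 106 evaluable. **Assumed, because the documents give no figure:** the fraction *c* of the delayed arm that receives the implant early, set at 5%, 10% and 20%.

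**1. The plan's own figures.** With (1.645 + 0.842)² ≈ 6.18:
- Aim 1: n = 2 × 18² × 6.18 / 8² = 62.6, so 63. Reproduced.
- Aim 2: n = 2 × 0.27 × 0.73 × 6.18 / 0.15² = 108.3, so 109. Reproduced.

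**2. Dilution.** Set the true effect of early insertion exactly at the margin, so that a non-inferiority claim is an error. Suppose each delayed-arm woman who crosses over takes on the early-arm outcome. The expected as-randomised difference is then (1 − c) × margin, and

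P(false non-inferiority) = Φ(c × margin / SE − 1.645).

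- Aim 1: SE = 18 × √(2/n), which is 3.207 h at n = 63 and 2.473 h at n = 106. At c = 10% and n = 63: Φ(0.8/3.207 − 1.645) = Φ(−1.396) = 8.1%.
- Aim 2: the early-arm rate is 0.12 and the delayed-arm rate is 0.27 − 0.15c. At c = 10% the delayed-arm rate is 0.255 and SE = √[(0.12 × 0.88 + 0.255 × 0.745)/109] = 0.0521, giving Φ(0.015/0.0521 − 1.645) = Φ(−1.357) = 8.7%.

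| Assumed crossover | Aim 1, 63 per arm | Aim 1, about 106 per arm | Aim 2, 109 per arm |
|---|---|---|---|
| 0% | 5.0% | 5.0% | 5.0% |
| 5% | 6.4% | 6.9% | 6.7% |
| 10% | 8.1% | 9.3% | 8.7% |
| 20% | 12.6% | 15.9% | 14.4% |

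**3. Check.** Adding the extra Aim 1 variance from mixing two means, c(1 − c) × 8², moves the 20% figures only to 12.5% and 15.8%. Simulation with 40,000 replicates gives 8.3% and 12.4% for Aim 1 at 63 per arm, and 9.2% and 15.0% for Aim 2, at 10% and 20% crossover. The formulas and the simulation agree to within about 1 point.

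**4. Power of an added treated-as-assigned comparison.** Take 106 in one arm and 106 × (1 − r) in the other, with no true difference. Power is Φ(0.15/√[0.27 × 0.73 × (1/n₁ + 1/n₂)] − 1.645) for Aim 2 and Φ(8/(18√(1/n₁ + 1/n₂)) − 1.645) for Aim 1. For r = 10%, 20% and 30% this gives 77%, 75% and 72% for Aim 2, and 93%, 92% and 90% for Aim 1.

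**5. Why the adherence definition matters.** If the delayed-arm set were limited to women who attend for insertion, and 43% did so, it would hold 0.43 × 106 ≈ 46 women. Power would fall to about 61% for Aim 2 and 81% for Aim 1.

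**The case against.** The strongest reply is that the protocol limits crossover. Eligibility requires willingness to use a non-hormonal bridging method until the implant can be placed. Women are told that, if they decline the trial, they can have the implant at any of the studied times. Those who consented by phone reaffirm before randomisation. The sentence on routine practice describes the service in general, and contraceptive counselling takes place at admission, normally before randomisation. No section says that delayed-arm women are offered early placement again. This stands: crossover is a risk, not an established fact, and its rate may be low. At 5% the inflation is modest.

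Three stronger readings are tempting, and the documents do not support them.
- **That the 43% attendance figure measures crossover.** It describes all women delivering at the hospital, not enrolled women with a booked visit. A delayed-arm woman who misses the visit has had no early exposure, so she does not make the arms alike.
- **That late insertion in the 30-minute arm dilutes every comparison.** A woman treated somewhat after 30 minutes is still exposed early. This affects mainly the contrast between the two early arms, which the calculation above does not model.
- **That the trial could not detect crossover from its own data.** The database is checked against the medical record, both early placements take place in hospital, and follow-up asks about the method. What can be said is that the protocol does not list insertion time as a variable or plan to use it.

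What remains after these concessions is that the plan specifies neither an analysis set nor a rule for insertion-time deviations, in a design where such deviations favour the claim.

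**Conclusion.** The concern holds as a cheap improvement. Both sample sizes reproduce, so nothing is wrong with the plan's arithmetic. The gap is that a non-inferiority claim on insertion timing would rest on a comparison by randomised arm with no planned comparison by treatment received. Even the as-randomised comparison is inferred from the wording of the aims, since intention-to-treat is not named.

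The direction of the bias follows from the design. Its size depends on three assumptions: the crossover rate, a true effect exactly at the margin, and crossover that is unrelated to a woman's breastfeeding prospects. Under these, 10% crossover takes the nominal 5% error to about 8–9%, and 20% takes it to about 13–16%. A reader might infer that the arms will in fact look alike, or that a finding of non-inferiority would be false. The documents support neither, because they report no crossover.

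**What to change.** 1. Record the actual insertion date and time, or that no implant was placed, for every woman, and report crossover by arm.
2. Keep the as-randomised comparison and name it. Add a pre-specified treated-as-assigned comparison for time to lactogenesis II and for 6-month breastfeeding, adjusted for delivery mode and the eligibility risk factors. Claim non-inferiority only if the two are consistent, and state beforehand what counts as consistent.
3. For analysis purposes only, define delayed-arm adherence by the absence of early insertion. For Aim 1 this means no implant before lactogenesis II; for Aim 2, no implant before the 6-week window. Women who miss the visit or never receive the implant then stay in the set.
4. Treat the contrast between the two early arms separately, and state how a first-arm insertion between 30 minutes and 24 hours is counted.

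The cost is one data field, one set definition and one further analysis per aim. Some power is lost, as shown in step 4 of the working, and the chance that both comparisons succeed cannot exceed that of the smaller set. The treated-as-assigned set is not fully protected by randomisation, and adjustment for a few covariates only partly repairs this. It should therefore support the as-randomised result, not replace it.

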#### *Analysis Plan*

The following outcomes will be evaluated using T-tests and include: exclusive breastfeeding continuation, any breastfeeding continuation, implant continuation. Additional secondary outcomes include side effects and tolerability of the implant, vaginal bleeding patterns, and contraceptive use. To evaluate these secondary outcomes between the two groups we will use the T-test, Wilcoxon Rank Sum test, Chi-squared test, or Fisher's exact test as appropriate.

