## Specific Aims

Our goal is to measure the impact of timing of postpartum contraceptive implant insertion on breastfeeding success and duration and to explore women's experiences with and attitudes towards contraceptive and breastfeeding counseling in the peripartum time period.

Specific Aim 1: To compare time to lactogenesis stage II among women randomized to receive the contraceptive implant within 30 minutes postpartum, 1-3 days postpartum and 6 or more weeks postpartum, utilizing a validated measure

Specific Aim 2: To assess rates of breastfeeding continuation, exclusivity, and satisfaction as well as device continuation and method satisfaction at 6 months postpartum among women who were randomized to receive the contraceptive implant within 30 minutes postpartum, 1-3 days postpartum and 6 or more weeks postpartum, utilizing a validated measure

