#### *Study Procedures*

Follow-up and data collection for participants in all three groups will be identical. In order to achieve specific aim 1, time to lactogenesis stage II will be measured based on maternal perception based on measures described and validated by Chapman et al and utilized in a similar study by Gurtcheff et al. Beginning on the first postpartum day,

subjects will be contacted daily. Subjects will be asked, "Has your milk come in? Some women experience this as a prickly feeling or tingling in the breast, dripping from the other nipple when nursing, milk running from the baby's mouth, or gulping by the baby." If the response is positive, women will then be asked, "When did your milk come in?" and the response recorded to the nearest hour. If lactogenesis has not occurred prior to hospital discharge, the patient will be contacted at least daily by their preferred method (phone, text or email) from study personnel until lactogenesis can be confirmed and recorded.

To achieve specific aim 2, women will complete study follow-up questionnaires at 6 weeks, 3 months and 6 months postpartum either by phone interview or by electronic web-survey, depending on the participant's preference. These questionnaires will assess breastfeeding status, exclusivity and satisfaction as well as contraceptive method continuation, satisfaction, and side effects, including bleeding. Women will be asked to contact the study coordinators when they stop breastfeeding or if they discontinue the contraceptive implant.

*Recruitment, Follow-up and Retention.*

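### The trial is sized as non-inferiority, but the Analysis Plan applies T-tests without a margin to breastfeeding continuation and gives no analysis for time to lactogenesis II

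*Combined protocol and SAP*

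**What the plan says.** Research Design and Study Subjects calls the trial a "three-armed randomized non-inferiority study". The Sample Size section supplies the non-inferiority terms. For Aim 1, "we chose a non-inferiority margin of an additional 8 hours to achieve lactogenesis II", "with a standard deviation in time to lactogenesis of up to 18 hours", at 80% power and one-sided 5%, giving 63 women per group. For Aim 2, "Assuming a non-inferiority margin of 15%, to achieve 80% power using a one-sided Type 1 error of 5" per cent, from a 6-month breastfeeding rate of 27%, giving 109 per group. Enrolment is set at 125 per group to allow for 15% loss.

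The first Specific Aim is "To compare time to lactogenesis stage II among women randomized to receive the contraceptive implant" at the three times. Study Procedures explains how the outcome is obtained: "In order to achieve specific aim 1, time to lactogenesis stage II will be measured based on maternal perception", "and the response recorded to the nearest hour".

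The Analysis Plan is three sentences long. It states "The following outcomes will be evaluated using T-tests and include: exclusive breastfeeding continuation, any breastfeeding continuation, implant continuation". The other two sentences list further secondary outcomes and a set of standard two-group tests for them.

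**The concern.** The margins justify the sample size, yet the analysis does not use them. There are two gaps.

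- **Aim 2.** Breastfeeding continuation is given a T-test with no margin, sidedness, confidence bound or rule for concluding non-inferiority. An unqualified T-test tests zero difference. Failing to reject zero difference is not evidence that the loss is smaller than 15 points. If a null result were read that way, the error would favour early placement.
- **Aim 1.** Time to lactogenesis II has its own aim, margin, sample size and hourly measurement, but no analysis. The estimator, the pairs of arms compared and the treatment of women who never reach lactogenesis (foreseen under Study Stopping Rules) are all open, and could be settled after the data are seen.

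**Working it through.** **1. The stated sizes are non-inferiority sizes.** The inputs are from Sample Size, with a true difference of zero, z(0.95) = 1.645 and z(0.80) = 0.842.

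- Aim 1: n = 2 × (18 × 2.487 / 8)² = 62.6, so 63 per group, as stated.
- Aim 2: n = 2 × 0.27 × 0.73 × 2.487² / 0.15² = 108.3, so 109 per group, as stated. The 15% margin is therefore 15 percentage points.

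**2. Evaluable number.** 125 × 0.85 = 106 per arm.

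**3. Aim 2: a difference test set against the margin rule.** Assumptions: 106 per arm, 27% in the 6-week arm, exact enumeration of both binomials. The margin rule is that the upper one-sided 95% bound for (6-week minus early) lies below 15 points. The two-sided column is included only because the Analysis Plan gives no sidedness.

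| True rates (6-week v early) | T-test non-significant, one-sided 5% | T-test non-significant, two-sided 5% | Margin met (Wald bound) |
|---|---|---|---|
| 27% v 12% | 12.3% | 20.1% | 5.3% |
| 27% v 17% | 45.4% | 57.7% | 22.8% |

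Farrington-Manning and Newcombe bounds give almost the same last column (5.1% and 5.3%; 22.7% and 22.9%).

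With 27% observed in the 6-week arm, the margin is met when the observed deficit is below about 5.3 points. The one-sided test is non-significant up to about 9.3 points (two-sided, about 11). Observed deficits of roughly 5 to 9 points are therefore non-significant and yet fail the margin.

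*Example.* 29/106 v 21/106:

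- Difference = 0.2736 − 0.1981 = 0.0755.
- SE = √[(0.2736 × 0.7264 + 0.1981 × 0.8019) / 106] = 0.0581.
- One-sided p = 0.10.
- Upper bound = 0.0755 + 1.645 × 0.0581 = 0.171, or 17.1 points, which is above 15.

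**4. Aim 1: the same comparison.** SD 18 h; SE = 18 × √(2/n). A difference is non-significant below 1.645 × SE (1.96 × SE two-sided) and non-inferior below 8 − 1.645 × SE.

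| Per arm | SE (h) | Non-significant below, one-sided (two-sided) | Non-inferior below | Power of margin test |
|---|---|---|---|---|
| 125 | 2.277 | 3.75 h (4.46 h) | 4.25 h | 97% |
| 106 | 2.472 | 4.07 h (4.85 h) | 3.93 h | 94% |

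The two rules nearly coincide, so the Aim 1 fault is the absent analysis and not a numerical gap between rules.

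**5. Is the rule supplied elsewhere?** Sample Size gives margins and levels but no estimator, comparison or conclusion rule. Study Procedures says how lactogenesis is measured, not how it is analysed. No other section contains analysis text.

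**The case against.** The strongest reply is that a T-test can be run against a margin. The design statement and Sample Size already fix the framework, margins and level, so the Analysis Plan may be read as incomplete rather than wrong. It is true that a shifted T-test is possible and that the margins and level are pre-stated. But the Analysis Plan does not say its tests are shifted, it sets them beside ordinary difference tests, and it refers to two groups in a three-arm trial. Followed literally, it tests zero difference. For Aim 1, no reading supplies a method, because the outcome is not named. The wording of the T-test sentence may leave its list of outcomes open, but an open list does not pre-specify an analysis.

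Three narrower points stand. The Aim 2 error rates are illustrative: they apply only if a null result were taken as non-inferiority, and the two-sided figures use a level the documents never mention. No numerical harm is shown for Aim 1. The choice among Wald, Farrington-Manning and Newcombe bounds makes little difference here; with no true difference they give 79.5%, 79.8% and 80.1% power at 106 per arm.

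**Conclusion.** The concern holds and should be fixed before analysis. As worded, the only analysis plan does not deliver the non-inferiority conclusions for which 63 and 109 women per group were calculated, and it omits the Aim 1 outcome.

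For Aim 2, a null result read as non-inferiority would accept a true 15-point loss in about 12% of trials instead of about 5%, and a true 10-point loss in about 45% instead of 23%. This rests on 27% in the 6-week arm, 106 evaluable per arm and a one-sided 5% test. For Aim 1 the conclusion rests on the omission alone.

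**What to change.** Amend the Analysis Plan before analysis, keeping the Sample Size margins and one-sided 5% level, for each early arm against the 6-week arm. The sponsor may add the 30-minute v 1–3-day comparison, since the Rationale raises that question.

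- **Aim 2.** Non-inferior if the upper one-sided 95% bound for the difference in 6-month breastfeeding proportion (6-week minus early; Farrington-Manning or Newcombe) is below 15 points. The sponsor should confirm whether continuation in the sample-size calculation means any breastfeeding.
- **Aim 1.** Non-inferior if the upper one-sided 95% bound for the difference in time to lactogenesis II (early minus 6-week) is below 8 hours, with a pre-stated handling of women who never reach it. One option is restricted mean time to a fixed cut-off, late enough not to shrink an 8-hour difference and with an SD compatible with the sizing.
- **Both.** State that a non-significant difference test is not a non-inferiority conclusion, and how the several comparisons combine into the trial's conclusion.

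The cost is wording only. Hourly lactogenesis times and 6-month breastfeeding status are already collected. At 106 per arm the Aim 2 margin test has about 80% power with no true difference. The Aim 1 test keeps 80% power up to an SD of 8 / (2.487 × √(2/106)) = 23.4 h (25.4 h at 125 per arm), against the 18 h assumed.

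A restricted-mean cut-off must stay within that limit. As an illustration, assume normal times with mean 60–72 h and SD 18 h, and 5% never reaching lactogenesis and set to the cut-off; the documents give neither a mean nor a failure rate. A 120 h cut-off then gives an SD of 20–22 h, which is acceptable. A 168 h cut-off gives 27–29 h, and power falls to about 63–69% at 106 per arm.
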